13.6 Cancel

A patient is deemed *cancel* if he/she is removed from the study for any reason before any study treatment is given. On-study material and the End of Active Treatment/Cancel Notification Form must be submitted. No further data submission is necessary.

13.7 Major Violation

A patient is deemed a major violation, if protocol requirements regarding treatment in cycle 1 of the initial therapy are severely violated that evaluability for primary end point is questionable. If the patient received treatment, the patient may continue treatment at the discretion of the physician as long as there are not safety concerns. The patient will continue in the Active Monitoring/Treatment phase of the study, as per section 4.0 of the protocol.

13.8 DLBCL

If a patient develops DLBCL at any time (except prior to end of cycle 1 of the combination treatment), it will be considered progressive disease. The patient will continue to survival follow-up per section 4.2. If the patient develops any other hematological malignancy while on study, it will not be considered progressive disease.

Note: Due to the nature of the disease, if the patient is diagnosed with DLBCL during the first cycle of treatment, it will be assumed that the DLBCL was present at registration. The patient will be deemed ineligible per Sec 3.27. Such a patient may continue treatment online protocol but will not be considered for statistical analysis for reporting.

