2.2 Secondary Goals

For Cohort 1

2.21 Determine the best overall response rate to treatment with daratumumab plus ibrutinib at any time during the course of the therapy.

2.22 The overall incidence of MRD (minimal residual disease) negative state and the time to achieving MRD negativity at any time during this therapy.

2.23 Progression free survival (as determined by the IWCLL criteria) among all patients.

2.24 The overall toxicity profile of daratumumab/ibrutinib treatment in this group of patients.

For Cohort 2

2.25 Determine the best overall response rate to treatment with daratumumab plus ibrutinib at any time during the course of the therapy.

2.26 The overall incidence of MRD (minimal residual disease) negative state and the time to achieving MRD negativity at any time during this therapy.

2.27 Progression free survival (as determined by the IWCLL criteria) among all patients.

2.28 The overall toxicity profile of daratumumab/ibrutinib treatment in this group of patients.

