3.2 Registration - Exclusion Criteria

3.21 Any serious medical condition, laboratory abnormality, or psychiatric illness that would prevent the subject from signing the informed consent form.

3.22 Patient is known to have **chronic obstructive pulmonary disease** with a forced expiratory volume in 1 second (FEV1) $<50\%$ of predicted normal (Note: FEV1 testing is required for subjects suspected of having chronic obstructive pulmonary disease and subjects must be excluded if FEV1 $<50\%$ of predicted normal.)

3.23 Patient is known to have **moderate or severe persistent asthma** within the past 2 years, or currently has uncontrolled asthma of any classification (Note: subjects who currently have controlled intermittent asthma or controlled mild persistent asthma are allowed in the study.)

3.24 Since this study involves an investigational agent whose genotoxic, mutagenic and teratogenic effects on the developing fetus and newborn are unknown, any of the following will deem the subject ineligible for the study:

- Pregnant women
- Nursing women
- Men or women of childbearing potential who are unwilling to employ adequate contraception

3.25 Any condition, including the presence of laboratory abnormalities, which places the subject at unacceptable risk if he/she were to participate in the study or confounds the ability to interpret data from the study.

3.26 Patients who have received **no prior therapy** for CLL.

3.27 Patients with history of any other cancer (except non-melanoma skin cancer or carcinoma in-situ of the cervix, unless in complete remission and off therapy for that disease for >3 years).

3.28 Patients who have **previously received daratumumab or any other anti-CD38 therapy** on a clinical trial or for any other malignancy.

3.29 Prior or current exposure to any of the following:

- Exposure to an investigational drug (including investigational vaccine) or invasive investigational medical device for any indication within 4 weeks or 5 pharmacokinetic half-lives, whichever is longer.
- Focal radiation therapy within 14 days prior to randomization with the exception of palliative radiotherapy for symptomatic management but not on measurable extramedullary plasmacytoma

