11.226 Hemoglobin $>11.0 \text{ gm/dl}$ or 50% increase over baseline without transfusions.

11.227 For patients whose only measurable disease at the time of enrollment is on CT scan, a CT scan demonstrating $> 50\%$ reduction of target nodes enlarged at baseline is required before classifying patients a PR.

11.23 **PROGRESSION (PD):** Patients will continue to receive protocol therapy unless they have evidence of disease progression according to the IWCLL criteria⁶ as evidenced by:

11.231 $\geq 50\%$ increase in the sum of the products of at least 2 lymph nodes on 2 consecutive determinations 2 weeks apart (at least one node must be ≥ 2 cm) or the appearance of new palpable lymph nodes >1.5 cm not due to a tumor flare. Enlargements or the appearance of new nodes due to a tumor flare do NOT qualify as progression.

11.232 $\geq 50\%$ increase in the size of the liver and/or spleen as determined by measurement below the respective costal margin on 2 consecutive determinations 2 weeks apart and with a minimum of a ≥ 2 cm increase in size from baseline; or appearance of hepatomegaly or splenomegaly which was not previously present at baseline and not due to a tumor flare.

11.233 Transformation to a more aggressive histology (e.g. Richter's transformation).

Note: If a patient develops DLBCL at any time, it will be considered disease progression. If the patient develops any other hematologic malignancy while on study, it will not be considered progressive disease.

11.234 $\geq 50\%$ increase in the absolute number of circulating lymphocytes NOT due to infection or tumor flare (taking as reference for progressive disease the smallest absolute lymphocyte count recorded since the treatment started). The absolute lymphocyte count must be at least 5000/mm³ to qualify as disease progression.

11.235 In the absence of progression as defined by 1, 2, 3, or 4 above, the presence of a ≥ 2 g/dl decrease in HGB, or $\geq 50\%$ decrease in platelet count, or absolute neutrophil count will NOT exclude a patient from continuing the study. Work-up of such decreases to exclude autoimmune hemolytic anemia, pure red cell aplasia, or idiopathic thrombocytopenic purpura (ITP) should be considered.

11.236 For patients who achieve a CR or nodular PR, progression will be defined as recurrence of circulating leukemia cell clone and an ALC >5000 or recurrence of adenopathy >1.5 cm not due to a tumor flare.

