16.322 The MRD response rate at any time during the course of treatment with daratumumab plus ibrutinib will be estimated by the number of patients who achieve MRD negative response in both blood and bone marrow at any time during combination treatment divided by the total number of evaluable patients. Exact binomial 95% confidence intervals for the true success rate will be calculated. In patients who achieve MRD negative response, time to achieve MRD negative response will be summarized descriptively (median, range). Time to achieve MRD negative response is defined as time from registration to the earliest date of documentation of MRD negative response in both blood and bone marrow.

16.323 Progression-free survival is defined as the time from registration to the earliest date of documentation of disease progression or death due to any cause. Patients who receive subsequent treatment for CLL before disease progression will be censored on the date of their last disease assessment prior to initiation of the subsequent treatment. The distribution of progression-free survival will be

estimated using the method of Kaplan-Meier.

16.324 Adverse Events: Platelets and hemoglobin will be graded according to the Grading Scale for Hematologic Adverse Events in CLL Studies in Appendix V. The maximum grade for each type of adverse event, regardless of causality, will be recorded and reported for each patient, and frequency tables will be reviewed to determine adverse event patterns. Adverse events will continue to be recorded and reported up to 30 days after the last day of study drug treatment.

16.34 Over Accrual: If more than the target number of patients are accrued, then the additional patients will not be used to evaluate the stopping rule or used in any decision making processes; however, they will be included in final point estimates and confidence intervals.

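### Section 13.8 removes treated patients with first-cycle DLBCL from all statistical analysis, while 11.233 counts DLBCL at any time as progression, no PFS population is named, and DLBCL in study Cycle 2 is coded two ways

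*Combined protocol and SAP*

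**What the plan says.** Two sections classify DLBCL. The note under 11.233 (within 11.2 Definitions) has no exception: "If a patient develops DLBCL at any time, it will be considered disease progression". Section 13.8 has one: "If a patient develops DLBCL at any time (except prior to end of cycle 1 of the combination treatment), it will be considered progressive disease".

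Its note then adds a presumption: "if the patient is diagnosed with DLBCL during the first cycle of treatment, it will be assumed that the DLBCL was present at registration". It follows that "The patient will be deemed ineligible per Sec 3.27", the criterion that excludes "Patients with history of any other cancer" with stated exceptions. The patient may stay on treatment, but the note ends: "Such a patient may continue treatment online protocol but will not be considered for statistical analysis for reporting". No endpoint is named, so read literally this covers response, PFS and adverse events.

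On PFS, goals 2.23 and 2.27 read: "Progression free survival (as determined by the IWCLL criteria) among all patients". Section 16.323 gives the definition, "Progression-free survival is defined as the time from registration to the earliest date of documentation of disease progression or death due to any cause", with a censoring rule for subsequent CLL treatment but no analysis population. For response, 16.311 makes eligibility a condition of being evaluable. Section 13.5 requires survival follow-up for ineligible patients who were treated, but asks for other data only up to the point where ineligibility is confirmed.

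**The concern.** The exclusion depends on something observed after treatment starts. It rests on a presumption that the disease was already there, not on a finding at registration, and the patients it removes are early failures by nature. If 13.8 is followed literally, the reported PFS curve does not describe everyone who was treated.

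Separately, the text does not settle how a Cycle 2 diagnosis is coded. Two analysts following different sections would record progression or no progression for the same patient. If this is left until cases are known, the choice would be made with the data in view.

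**Working it through.** **1. The windows side by side.** Inputs: 28-day cycles (7.1); ibrutinib is added at study Cycle 2 (7.0); six combination cycles end at Cycle 7 (16.11). So cycle 1 of the combination is normally study Cycle 2.

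| DLBCL diagnosed in | Note to 11.233 | 13.8, opening sentence | 13.8, note |
|---|---|---|---|
| Study Cycle 1 (about days 1 to 28) | Progression | Exempt | Ineligible, not analysed |
| Study Cycle 2 (about days 29 to 56) | Progression | Exempt | Not covered, if the note means study Cycle 1 |
| Study Cycle 3 onward | Progression | Progression | Not covered |

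For patients who start both drugs in Cycle 1, as 7.0 allows with approval, the two windows in 13.8 coincide and the middle row does not arise.

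**2. The primary rules.** The plan's figures reproduce. Cohort 1: P(X ≥ 3 | 22, 0.05) = 0.0948 (printed 0.09) and P(X ≥ 3 | 22, 0.20) = 0.8455 (printed 0.85). Cohort 2: P(X ≥ 17 | 26, 0.50) = 0.0843 (printed 0.08) and P(X ≥ 17 | 26, 0.75) = 0.9091 (printed 0.91). Both rules are stated for evaluable patients, and 16.12 plans two spare patients per cohort for ineligibility and other losses. Leaving out ineligible patients changes none of these figures.

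**3. Effect on PFS.** Let n be the patients analysed (22 or 26) and m the treated patients dropped and replaced. The documents give no DLBCL rate, so m = 0, 1 or 2 is assumed; 2 would use all the spare accrual. With no censoring before the dropped events, at any later time

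KM(excluding) / KM(all treated) = (n + m) / n.

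- Cohort 2: 27/26 = 1.038; 28/26 = 1.077.
- Cohort 1: 23/22 = 1.045; 24/22 = 1.091.
- m = 0: ratio 1.

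Illustrations: an all-treated PFS of 75% in Cohort 2 (the 26-month single-agent figure in section 1.2, borrowed only for scale) would be reported as 0.75 × 27/26 = 77.9% or 0.75 × 28/26 = 80.8%. An assumed 50% in Cohort 1 would be reported as 0.50 × 23/22 = 52.3% or 0.50 × 24/22 = 54.5%.

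Section 16.34 brings over-accrued patients into final estimates, which shrinks the ratio slightly. With all 28 Cohort 2 places filled and one case dropped it is 28/27 = 1.037.

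**4. Response, if these patients were added as non-responders.** At the success thresholds, 17/26 = 65.4% becomes 17/27 = 63.0% or 17/28 = 60.7%, and 3/22 = 13.6% becomes 3/23 = 13.0% or 3/24 = 12.5%.

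**5. Power, if m such patients sat inside the fixed n as non-responders.** Cohort 2 at 75%: P(X ≥ 17 | 26 − m, 0.75) = 0.909, 0.851, 0.766 for m = 0, 1, 2. Cohort 1 at 20%: P(X ≥ 3 | 22 − m, 0.20) = 0.846, 0.821, 0.794. This matters for the choice of window below.

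**The case against.** The best defence is that 13.8 is a specific rule qualifying a general one. The note to 11.233 speaks of a patient who develops DLBCL. If first-cycle disease is presumed present at registration, it did not develop on study, and the patient is simply ineligible, a status that 13.5 and 16.12 provide for. This is a fair reading for study Cycle 1 and fully justifies the response set. It does not reach Cycle 2, where 11.233 and the opening sentence of 13.8 still disagree. Nor does it settle PFS, for which no eligibility-based set is defined.

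Second, a goal that covers all patients does not literally say all treated patients. It could mean all eligible patients, as opposed to responders only. That stands: a reader might infer that the plan demonstrably breaches its own PFS goal, but the text supports only an unspecified population together with an exclusion rule that conflicts with the broader reading. Upward bias is therefore a statement relative to an all-treated PFS.

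Third, the effect is small. Ignoring censoring, the standard error at 75% with n = 26 is √(0.75 × 0.25/26) = 8.5 points, so one case moves the Cohort 2 estimate by 2.9 points, about 0.34 standard errors. At 50% with n = 22 it is √(0.50 × 0.50/22) = 10.7 points, against a shift of 2.3, about 0.2 standard errors. PFS is descriptive here, with no test or threshold. This also stands.

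Fourth, the note in 13.8 directly follows an exception running to the end of combination cycle 1 and may have been meant to explain that same window. The text does not decide this, so the remedy must leave the choice to the sponsor.

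**Conclusion.** The point holds as an inconsistency in analysis rules. Section 13.8 excludes without limit what 11.233 counts as an event, 16.323 does not say who is in the PFS analysis, and on the standard schedule a Cycle 2 diagnosis has two codings. It should be corrected before analysis, but it is not a flaw in the primary design. The size depends on an assumed count of cases and on no censoring before the early events.

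Two stronger conclusions are tempting and not supported. A reader might infer that the primary error rates are inflated. That would require reading the null rates as rates among all treated patients, whereas the decision rules and 16.311 refer to evaluable patients. A reader might also infer that safety data on these patients go uncollected. Sections 10.82, 10.88 and 16.324 require adverse events to be recorded and reported. What remains on safety is narrower: the unrestricted wording of 13.8 conflicts with patient-by-patient reporting in 16.324, and 13.5 sits awkwardly with a patient who stays on treatment after ineligibility is confirmed.

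**What to change.** 1. In 13.8, restrict the exclusion to the evaluable set for the primary response decision rule.
2. Use one window, named by protocol cycle number, in 11.233 and in both parts of 13.8, with the sponsor stating which cycle is meant. If the note means study Cycle 1, naming that cycle leaves the evaluable set as it is. If it was meant to run to the end of combination cycle 1, naming study Cycle 1 would move Cycle 2 cases into the evaluable set as non-responders, at the power cost in step 5 of the working (Cohort 2: 0.909 to 0.851 for one case).
3. In 16.323, state that PFS includes every treated patient, with DLBCL diagnosed after the first dose as an event on its diagnosis date. Show the version without first-cycle DLBCL as a sensitivity analysis.
4. Keep these patients in the safety tables under 16.324, and amend 13.5 so that data continue to be submitted for ineligible patients who remain on treatment.
5. Optionally, report a sensitivity response rate that counts them as non-responders.

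The cost is a slightly less favourable PFS if cases occur and a little more data submission. The 22- and 26-patient rules are unchanged, subject to the choice in item 2. Survival follow-up of ineligible treated patients is already required by 13.5.

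Whether treatment continues after DLBCL is a clinical matter on which 13.8 differs from 11.23 and 13.2. The sponsor must reconcile those passages; no rule is proposed here.

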14.0 Body Fluid Biospecimen

None.

15.0 Drug Information

15.1 Daratumumab (Darzalex®, Darzalex Faspro™, JNJ-54767414)

Please consult the most current Investigator's Brochure and package insert for complete drug information.

15.11 **Background:** Daratumumab is an immunoglobulin G1 kappa (IgG1κ) human monoclonal antibody against CD38 antigen, produced in a mammalian cell line (Chinese Hamster Ovary [CHO]) using recombinant DNA technology. The molecular weight of daratumumab is approximately 148 kDa.

CD38 is a transmembrane glycoprotein (48 kDa) expressed on the surface of hematopoietic cells, including multiple myeloma and other cell types and tissues and has multiple functions, such as receptor mediated adhesion, signaling, and modulation of cyclase and hydrolase activity. Daratumumab is an IgG1κ human monoclonal antibody (mAb) that binds to CD38 and inhibits the growth of CD38 expressing tumor cells by inducing apoptosis directly through Fc mediated cross linking as well as by immune-mediated tumor cell lysis through complement dependent cytotoxicity (CDC), antibody dependent cell mediated cytotoxicity (ADCC) and antibody dependent cellular phagocytosis (ADCP). Myeloid derived suppressor cells (MDSCs) and a subset of regulatory T cells (CD38+Tregs) expresses CD38 and is susceptible to daratumumab mediated cell lysis.

15.12 Formulation:

- SC formulation: Daratumumab and hyaluronidase-fihj injection is a sterile, preservative-free, colorless to yellow, and clear to opalescent solution supplied in a single-dose vial for subcutaneous administration. Each 15 mL single-dose vial contains 1800 mg daratumumab and 30,000 units hyaluronidase, histidine, sorbitol, methionine, polysorbate 20, and sterile water for injection with a pH of 5.6.

15.13 Preparation and storage:

- Study drug labels will contain information to meet the applicable regulatory requirements.

All Daratumumab SC study drug vials must be stored in the original carton in a refrigerator ranging from 2°C to 8°C and must not be utilized after the expiry date printed on the label. The product must be protected from light and must not be frozen. Daratumumab SC does not contain preservatives; therefore, any unused portion remaining in the vial must be discarded.

Daratumumab and hyaluronidase-fihj SC injection is directly drawn from the vial into a syringe and is compatible with polypropylene or polyethylene syringe material; polypropylene, polyethylene, or polyvinyl chloride (PVC) subcutaneous infusion sets; and stainless steel transfer and injection needles. Vials should be removed from the refrigerator and allowed to equilibrate to ambient temperature (15°C to 30°C). Store the unpunctured vial at ambient temperature for a maximum of 24 hours. Withdrawn 15mL from the vial into a syringe. After the solution is withdrawn into the syringe, replace the transfer needle with a syringe cap. To avoid needle clogging, attach the

hypodermic injection needle or subcutaneous infusion set to the syringe immediately prior to injection. If not used immediately, store the withdrawn solution for up to 4 hours at ambient temperature and light.

15.14 Administration:

- Administer pre-infusion and post-infusion medications. Refer to section 7 of the protocol.
- SC administration: Utilizing a hypodermic injection needle or subcutaneous infusion set, inject 15 mL of the daratumumab and hyaluronidase-fihj solution into the subcutaneous tissue of the abdomen approximately 3 inches to the right or left of the navel over approximately 3-5 minutes. Rotate injection sites for successive injections. Never inject DARZALEX FASPRO into areas where the skin is red, bruised, tender, hard or areas where there are scars. Pause or slow down delivery rate if the patient experiences pain. In the event pain is not alleviated by pausing or slowing down delivery rate, a second injection site may be chosen on the opposite side of the abdomen to deliver the remainder of the dose. During treatment with DARZALEX FASPRO, do not administer other medications for subcutaneous use at the same site as DARZALEX FASPRO. No data are available on performing the injection at other sites of the body

15.15 Pharmacokinetic information for administration:

SC daratumumab and hyaluronidase-fihj Administration:

Following the administration of the recommended dose of 1,800 mg daratumumab and 30,000 units hyaluronidase subcutaneously once weekly for 8 weeks, the mean \pm standard deviation (SD) maximum trough concentrations (C_{trough} following the 8th dose) were 593 \pm 306 μ g/mL compared to 522 \pm 226 μ g/mL for daratumumab 16 mg/kg administered intravenously, with a geometric mean ratio of 108% (90% CI: 96, 122). The estimated median daratumumab area under the concentration-time curves (AUC₀₋₇ days) and daratumumab peak concentration (C_{max}) following the 8th dose were comparable between subcutaneous and intravenous daratumumab (4017 μ g/mL \cdot day vs. 4,019 μ g/mL \cdot day for AUC₀₋₇ days and 592 μ g/mL vs. 688 μ g/mL for C_{max}). The absolute bioavailability of daratumumab-hyaluronidase is 69%, with peak concentrations occurring around 3 days (T_{max}). The estimated mean (coefficient of variation, CV) volume of distribution for the central compartment is 5.2 L (37%) and peripheral compartment was 3.8 L with the daratumumab-hyaluronidase formulation. Daratumumab is cleared by parallel linear and nonlinear saturable target mediated clearances. The estimated mean (CV%) linear clearance of daratumumab is 119 mL/day. The estimated mean (CV%) elimination half-life associated with linear clearance is 20 days (22%).

As expected with subcutaneous administration, concentration-time curves following administration in all cohorts indicate a later T_{max} of approximately 72h post-dose, compared with IV administration when T_{max} occurs at or near the end of infusion. The range of C_{3D1} C_{trough} observations for the SC cohort is within the range observed following 16 mg/kg IV dosing, and the variability appeared to be similar for the daratumumab SC and 16 mg/kg IV cohorts. The observed C_{max} values from the daratumumab SC cohort is within the range observed for daratumumab 16 mg/kg IV.

Special Populations

Pediatric Use: The safety assessment in pediatric participants is based on the limited safety data from analysis of the PK, safety and efficacy of combination daratumumab at 16 mg/kg IV in pediatric and young adult participants (1 to <30 years of age) with relapsed/refractory B-cell ALL and T-cell ALL/LL. Based on PK analysis, exposure in this population was within the exposure range for adult participants with MM and was similar across all age subgroups.

Hepatic Impairment: Population PK analysis demonstrated no clinically important differences in the exposure to daratumumab were observed between patients with normal hepatic function and mild hepatic impairment in studies of both daratumumab IV and SC. There were few patients with moderate-severe hepatic impairment to make meaningful conclusions for these populations..

15.16 **Potential Drug Interactions:** Clinical PK assessments with SC formulations and lenalidomide, bortezomib, thalidomide, pomalidomide, melphalan, prednisone, cyclophosphamide, dexamethasone, and carfilzomib indicated no clinically relevant drug-drug interactions.

Effects on laboratory tests:

Interference with Indirect Antiglobulin Tests: Daratumumab binds to CD38 on RBCs and interferes with compatibility testing, including antibody screening and cross matching and may persist for up to 6 months after the last daratumumab administration. Daratumumab interference mitigation methods include treating reagent RBCs with dithiothreitol (DTT) to disrupt daratumumab binding or genotyping. Since the Kell blood group system is also sensitive to DTT treatment, K-negative units should be supplied after ruling out or identifying alloantibodies using DTT-treated RBCs. If an emergency transfusion is required, non-cross matched ABO/RhD compatible RBCs can be given per local blood bank practices.

Interference with Serum Protein Electrophoresis and Immunofixation Tests: Daratumumab may be detected on serum protein electrophoresis (SPE) and immunofixation (IFE) assays used for monitoring disease monoclonal immunoglobulins (M protein). This can lead to false positive SPE and IFE assay results for patients with IgG kappa myeloma protein impacting initial assessment of complete responses by International Myeloma Working Group (IMWG) criteria. In patients with persistent very good partial response, where daratumumab interference is suspected, consider using a FDA approved daratumumab-specific IFE assay to distinguish daratumumab from any remaining endogenous M protein in the patient's serum, to facilitate determination of a complete response.

15.17 **Known potential toxicities:**

Very common known potential toxicities, $\geq 10\%$:

Injury, poisoning, and procedural complications: infusion related reaction
 Infections and infestations: upper respiratory tract infection, bronchitis, pneumonia,
 Blood and lymphatic system disorders: neutropenia, thrombocytopenia, anemia, lymphopenia, leukopenia

Nervous system disorders: headache peripheral sensory neuropathy, headache, paresthesia
 Metabolism and nutrition disorders: decreased appetite
 Respiratory, thoracic, and mediastinal disorders: cough, dyspnea,
 Musculoskeletal and connective tissue disorders: back pain, arthralgia
 General disorders and administration site conditions: fatigue, pyrexia, peripheral edema, asthenia

Common known potential toxicities, 1% - <10%:

Cardiac disorders: atrial fibrillation
 Gastrointestinal disorders: pancreatitis
 General disorders and administration site conditions: injection site reaction, chills
 Immune system disorders: hypogammaglobulinemia
 Infections and infestations: urinary tract infection, influenza, sepsis
 Metabolism and nutrition disorders: hypokalemia, hyperglycemia, dehydration
 Musculoskeletal and connective tissue disorders: musculoskeletal chest pain
 Respiratory, thoracic, and mediastinal disorders
 hypoxia, pulmonary edema
 Vascular disorders: hypertension
 Skin and subcutaneous tissue disorders: pruritis

Uncommon and rare known potential toxicities, <1%:

Infections and infestations: cytomegaloviral infection, hepatitis B reactivation,
 Respiratory, thoracic, and mediastinal disorders: laryngeal edema

Daratumumab SC studies demonstrated that the incidence of anti-daratumumab antibodies was low [<1%] following daratumumab administration in multiple myeloma (SC) and amyloidosis (SC) participants. Treatment emergent anti-rHuPH20 antibodies developed in 7.1% (60/840) of participants who received daratumumab SC in monotherapy and combination clinical studies.

Hepatitis B virus (HBV) reactivation, in some cases fatal, have been reported in patients treated with daratumumab. HBV screening should be performed in all patients before initiation of treatment with daratumumab and as clinically indicated. Treatment interruption may be warranted in the event of HBV reactivation while on daratumumab.

Please refer to the Investigator Brochure and package insert for a more comprehensive list of treatment-emergent adverse events.

15.18 **Drug procurement:** Daratumumab (Darzalex®, Darzalex Faspro®) commercially available

15.19 **Nursing Guidelines:**

1. Daratumumab can cause severe infusion reactions, usually during the first infusion. Patients who have experienced a reaction may experience further reactions with subsequent infusions. Most reactions occur during or within 4 hours of infusion, however may occur up to 48 hours after an infusion. Warn patient of this possibility. Monitor patient throughout infusion for bronchospasm, hypoxia, SOB, and hypertension. Patients may also

experience symptoms of anaphylaxis. Administer emergency medication as ordered.

2. Patients may experience infections, including URI and pneumonia. Patients who have an ongoing infection should not receive agent.
3. Patients may experience gastrointestinal side effects including diarrhea and nausea. Treat symptomatically and monitor for effectiveness.
4. Warn patients about the possibility of peripheral neuropathy, dizziness, and insomnia.
5. Fatigue is common. Instruct patient in energy conserving lifestyle.
6. Rarely patients may experience cardiac issues including, atrial-fibrillation, peripheral edema, and hypertension. Instruct patient to report any chest pain, heart palpitations, and swelling to the study team.
7. Monitor CBC w/diff as cytopenias (thrombocytopenia, neutropenia, anemia, and lymphopenia) have been seen. Instruct patient to report any unusual, bruising, bleeding and/or infections/fever to the study team.
8. If using SC, injection should be in the abdomen over 3-5 minutes. There is no data on SC injections on other parts of the body.

